| ECOG performance status | 8.3.2 | X | X | | | X | | | X | X |
| Height | 8.3.3 | X | | | | | | | | |
| Weight | 8.3.3 | X | X | X | X | X | X | X | X | X |
| Vital signs (BP, HR, RR, Temp) | 8.3.4 | X | X | X | X | X | X | X | X | X |
| Disease assessment ² | 8.1 | X | 6 weeks and 15 weeks after C1D1, then every 8 weeks | | | | | | X ³ | Every 12 weeks until 1 year from EOT, then every 6 months until disease progression up to 2 years from EOT |
| Hematology and Chemistry | 8.3.5 | X | X ⁴ | X | | X ⁴ | X | | X | X |
| Coagulation and Urinalysis | 8.3.5 | X | | | | | | | | |
| TSH (reflex free T3 or free T4) | 8.3.5 | X | X | | | X | | | X | X |
| Hepatitis B, C, and HIV tests | 8.3.5 | X | | | | | | | | |

| | Protocol Section | Screening | Treatment Period | | | | | | EOT | Follow-up Period (up to 2 years from EOT) Every 12 weeks |
|--|------------------|-----------|---|------------------|----|--|---|------------------|--|--|
| | | | Cycle 1 (3 week cycle) | | | Cycle 2 (6 week cycle) ⁹ | | | | |
| Day (D) | | -28 to -1 | 1 | 8 | 15 | 1 | 8 | 15 | 1 | |
| Pregnancy test, if applicable | 8.3.6 | X | X ⁴ | | | X | | | X | X |
| 12-lead ECG ⁵ | 8.3.7 Table 4 | X | X (pre-dose, EOI, and 4 hr post-dose) | X (post-dose) | X | X (pre-dose, EOI, and 4 hr post-dose) | X | X (post-dose) | X ¹¹ | X |
| Premedication | 6.7.1 | | D-1 to D2 | | | D-1 to D2 | | | D-1 to D2 for cycles containing loncastuximab tesirine | |
| Loncastuximab tesirine administration | 6.3.1 | | X | | | X | | | D8 of Cycles 5 and 6 for patients who are PR or SD at Week 15 evaluation | |
| Durvalumab administration | 6.3.2 | | | X | | | | X | X ⁸ | |
| Loncastuximab tesirine PK ⁵ sample | 8.4.1 Table 5 | | X ⁵ (pre-dose, EOI, and 4 hr post-dose) | X | X | X (pre-dose, EOI, and 4 hr post-dose) | X | X | X ⁶ (pre-dose) | X |
| Loncastuximab tesirine ADA ⁵ sample | 8.4.1 Table 5 | | X ⁵ (pre-dose) | | X | X (pre-dose) | | | X ⁶ (pre-dose) | X ⁷ |

| | Protocol Section | Screening | Treatment Period | | | | | | EOT | Follow-up Period (up to 2 years from EOT) Every 12 weeks |
|---|------------------|--|---------------------------|---|----|--|---|-----------------|-----|--|
| | | | Cycle 1 (3 week cycle) | | | Cycle 2 (6 week cycle) ⁹ | | | | |
| Day (D) | | -28 to -1 | 1 | 8 | 15 | 1 | 8 | 15 | 1 | |
| Durvalumab PK sample | 8.4.1 | | | | | | | X ¹⁰ | | |

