| Concomitant medications | 6.7.6 | From ICF signature date or D-14, whichever is earlier, until 30 days after last dose of study drug(s) | | | | | | | | |
| Adverse events | 8.2 | AE/SAEs from ICF signature date within 30 days after last dose of study drug(s); thereafter, related SAEs only | | | | | | | | |
| 1 st New anti-cancer treatment | | | | | | | | | X | X |
| Survival | | | | | | | | | X | X |

Abbreviations: ADA: anti-drug antibody; AE: adverse events; BP: blood pressure; ECG: electrocardiogram; ECOG: Eastern Cooperative Oncology Group; EOI: end of infusion; EOT: end of treatment; HR: heart rate; ICF: informed consent form; PK: pharmacokinetics; RR: respiratory rate; SAE: serious AE; Temp: temperature; wks: weeks

Visit Scheduling Windows:

- Treatment Period: Visit day ± 2 days (excluding C1D1 which is the reference day).
- EOT: As soon as possible after decision to discontinue the study drug(s) but preferably within 30 days after last dose of study drug(s) unless a new anticancer treatment is planned to be administered before the 30 days, in which case EOT should be conducted before initiation of the new anticancer treatment.
- Follow-up Period: Visit day ± 14 days.

¹ Tumor biopsy should be obtained prior to study drug administration.

² Screening imaging (PET-CT) must be performed within 4 weeks prior to C1D1 and the same assessment method should be used throughout the study. Week 6 imaging should be performed prior to C3D1 and Week 15 imaging should be performed prior to C5D1. All other imaging for disease assessment for patients on study drug(s) should be performed within ± 2 weeks of the scheduled timepoint. Disease assessments should be performed at the timepoints specified even if study drug dosing is delayed. If a scan has been performed within 8 weeks of EOT, it does not need to be repeated at EOT.

³ Disease assessments to be performed in patients having discontinued study drug(s) for reasons other than disease progression.

⁴ Not needed if screening assessment was performed within 3 days prior to C1D1.

⁵ On days when loncastuximab tesirine is administered, ECG, PK, and ADA timepoints are in relation to loncastuximab tesirine dose.

⁶ Cycle 3, C5, C6, C7; see [Table 5](#).

⁷ Patients who test positive for loncastuximab tesirine ADAs may be requested to supply additional ADA samples as specified in the protocol, [Section 8.4.2](#).

⁸ Administration of durvalumab, C3D1 will be 4 weeks after C2D15.

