6.5 Dose Delays and Modifications

6.5.1 Loncastuximab Tesirine

If a patient experiences any Grade ≥ 3 (≥ 2 for edema, effusion, or increased AST/ALT/GGT) toxicity, loncastuximab tesirine must be held until the toxicity resolves to Grade 1 or less (Grade 1 or baseline for peripheral neuropathy). If loncastuximab tesirine dosing is delayed by more than 3 weeks and the toxicity is considered at least possibly related to loncastuximab tesirine, then subsequent doses of loncastuximab tesirine will be reduced by 50%.

In addition, the Investigator may reduce the dose of loncastuximab tesirine by 50% for any Grade ≥ 3 (≥ 2 for edema, effusion, or increased AST/ALT/GGT) toxicity that is possibly related to loncastuximab tesirine but does not result in dosing delay of more than 3 weeks if they feel it is in the best interest of the patients.

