6.5.2 Durvalumab

If a patient experiences any Grade ≥ 3 toxicity, durvalumab must be held until the toxicity resolves to Grade 1 or less (Grade 1 or baseline for peripheral neuropathy).

In addition, durvalumab must be held for the following Grade ≥ 2 specific immune-mediated toxicities:

- Pneumonitis/ILD
- Diarrhea/Colitis
- Hepatitis (elevated liver function tests)
- Nephritis or renal dysfunction
- Persistent rash (>1 -2 weeks)
- Endocrinopathy (except isolated hypothyroidism or Type 1 diabetes mellitus)
- Neurotoxicity
- Peripheral neuromotor syndromes
- Myocarditis
- Myositis/polymyositis

See [Section 13.3](#), [Appendix 3](#) for guidelines regarding management and resumption of durvalumab therapy after specific immune-mediated toxicities.

For all other toxicities, durvalumab must be held until the toxicity resolves to Grade 1 or less (Grade 1 or baseline for peripheral neuropathy).

Durvalumab will be given at full dose when resumed after being held for toxicity, i.e., there will be no dose reduction.

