8.3 Safety Assessments

Safety will be assessed based on the procedures in the subsection below. AE/SAE collection and reporting is described in [Section 8.2](#).

Unless otherwise specified, all safety assessments on dosing days will be done prior to administration of study drug(s).

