8.3.4 Vital Signs

Vital signs include the measurements of arterial blood pressure (systolic and diastolic), heart rate, respiratory rate, and body temperature and should be performed according to the institutional standards, see timepoints shown on Table 1. Vital signs should be measured before and after each loncastuximab tesirine infusion and each durvalumab infusion.

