8.3.5 Laboratory Tests

Samples will be collected at the time points specified as per SoE (Table 1).

Hematology: white blood cells (WBCs) with 5-part differential (neutrophils, eosinophils, basophils, lymphocytes, and monocytes), platelet count, hemoglobin, and hematocrit.

Chemistry: ALT, AST, GGT, ALP, amylase, lipase, total bilirubin (conjugated and unconjugated bilirubin only when total is abnormal), sodium, potassium, chloride, phosphate/phosphorus, calcium, magnesium, blood urea nitrogen or urea, carbon dioxide/bicarbonate, creatinine, creatine phosphokinase, total protein, albumin, glucose and lactate dehydrogenase.

Coagulation: partial thromboplastin time and International Normalized Ratio.

Urinalysis: pH, specific gravity, protein, WBC, red blood cell (RBCs), ketones, glucose, and bilirubin.

Urinalysis may be performed by dipstick. Abnormal findings should be followed up with a microscopic evaluation and/or additional assessments as clinically indicated. A microscopic evaluation consists at a minimum of WBC and RBC quantitation per high power field, as well as semi-quantitative assessment of other cells and substances, if present, such as epithelial cells, bacteria, and crystals (“few,” “moderate,” “many”). Other evaluations depending on microscopic findings may be added.

Other Tests: TSH, (reflex free T3 or free T4). Hepatitis B, C, and HIV.

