8.4.1 Pharmacokinetics

The PK concentrations of loncastuximab tesirine (total antibody), PBD-conjugated antibody, and unconjugated warhead SG3199 will be assessed by a central laboratory designated by the Sponsor using validated bioanalytical methods.

Approximately 6 mL of whole blood will be collected as per Table 1 and Table 5. Blood should be drawn from a vein away from the one used for study drug infusion.

PK samples must be stored at -70°C. Please refer to the laboratory manual for detailed instructions regarding specimen handling and shipment.

PK blood collection should occur immediately after the end of the ECG recording and, when applicable, after vital signs. If a patient experiences Torsade de Pointes, additional PK samples (e.g., unscheduled) should be collected.

Table 5 Sampling Schedule for Loncastuximab Tesirine PK and ADA

| Cycle | Day | PK timepoint (window) | ADA timepoint (window) |
|--------------|-----|---|--|
| C1 | D1 | Pre-dose (preferably within 2 h prior to start of infusion) EOI (-5 to +10 min) Post-dose* 4 h (\pm 10 min) | Pre-dose (preferably within 2 h prior to start of infusion) |
| | D8 | Post-dose* 168 h (\pm 48 h) | - |
| | D15 | Post-dose* 336 h (\pm 48 h) | Post-dose* 336 h (\pm 48 h) |
| C2 | D1 | Pre-dose (within 2h prior to start of infusion) EOI (-5 to +10 min) Post-dose* 4 h (\pm 10 min) | Pre-dose (within 2 h prior to start of infusion) |
| | D8 | Post-dose* 168 h (\pm 48 h) | - |
| | D15 | Post-dose* 336 h (\pm 48 h) | - |
| C3 | D1 | Pre-dose (preferably within 2 h prior to start of infusion) | Pre-dose (preferably within 2 h prior to start of infusion) |
| C5, C6, C7** | D1 | Pre-dose (preferably within 2 h prior to start of infusion) | Pre-dose (preferably within 2 h prior to start of infusion) |
| EOT | | At any time during visit day | At any time during visit day |
| Unscheduled | | Any time | Any time (if applicable, close to PK sample) |

Abbreviations: ADA, anti-drug antibody; EOI, end of infusion; EOT, end of treatment; PK, pharmacokinetics.

*Post-dose timepoint is counted from start of loncastuximab tesirine infusion.

**Only for patients who receive loncastuximab tesirine during Cycles 5 and 6.

Blood samples for determination of durvalumab concentration in serum will be obtained according to the SoE, [Table 1](#). The PK concentration of durvalumab prior to the C2D15 dose will also be assessed by a central laboratory designated by the Sponsor using a validated bioanalytical method.

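### Table 1 schedules no same-day hematology/chemistry for three infusions: durvalumab dose 2 (C2D15) and optional loncastuximab doses 3 and 4 (C5D8, C6D8)

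*Protocol*

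**What the plan says.** The hematology and chemistry row of Protocol Table 1 is marked at screening, C1D1, C1D8, C2D1, C2D8, Day 1 of Cycle 3 and beyond, and end of treatment. The C1D15 and C2D15 cells are empty. At C1D1 a screening panel no more than 3 days old may stand in.

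Durvalumab is given on C1D8, C2D15 and Day 1 of each later cycle (Table 1; Sections 4.3 and 6.3.2). Loncastuximab is given on C1D1 and C2D1, with two optional further doses on "D8 of Cycles 5 and 6 for patients who are PR or SD at Week 15 evaluation". After Cycle 2 the only visit column is Day 1. Table 5 likewise lists only Day 1 sampling for Cycles 5 to 7, with the note "Only for patients who receive loncastuximab tesirine during Cycles 5 and 6".

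On laboratory timing, Section 8.3.5 says "Samples will be collected at the time points specified as per SoE" and goes no further. Section 8.3 only puts dosing-day assessments before the dose. Section 8.3.4 treats vital signs differently: "Vital signs should be measured before and after each loncastuximab tesirine infusion and each durvalumab infusion".

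The dose rules depend partly on laboratory values. Under 6.5.1, after a Grade 3 or higher toxicity, or Grade 2 or higher for AST, ALT or GGT, "loncastuximab tesirine must be held until the toxicity resolves to Grade 1 or less". Under 6.5.2, "durvalumab must be held for the following Grade" 2 or higher immune-mediated toxicities, a list that includes elevated liver tests and renal dysfunction.

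**The concern.** A mandatory hold works only if its trigger is looked for when the dosing decision is made. Edema, rash or dyspnea can be seen at the visit. A rise in transaminases, GGT or creatinine, or a fall in counts, may give no sign. At these three infusions a site can follow the schedule exactly and dose without a current panel.

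The relevant abnormalities are not rare with loncastuximab. Section 1.2.2 reports, for the Phase 1 study, GGT increase in 26.4% of patients (Grade 3 or higher in 14.6%), and Grade 3 or higher decreases in neutrophil count in 16.0% and platelet count in 11.8%. Those are rates over the whole of that study, not rates for any 7-day interval.

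In Cycles 5 and 6 there is a further point. The Day 1 panel is drawn before that day's durvalumab, so no scheduled panel lies between that infusion and the loncastuximab dose a week later. Doses 3 and 4 are also weight-based, with no weight scheduled on the day.

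**Working it through.** **Inputs.** Cycle 1 lasts 21 days, Cycle 2 lasts 42 days and later cycles last 28 days (Section 4.3). Treatment-period visits may move by 2 days either way, with C1D1 fixed (Table 1, visit windows). Laboratory and infusion visits are those listed above.

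**Calendar.** With C1D1 = Day 1:

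- C2D1 = 1 + 21 = 22; C2D8 = 29; C2D15 = 36
- C3D1 = 22 + 42 = 64
- C4D1 = 92; C5D1 = 120; C6D1 = 148; C7D1 = 176
- C5D8 = 127; C6D8 = 155

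As a check, C2D15 to C3D1 is 64 − 36 = 28 days, the 4 weeks stated in Table 1 footnotes 8 and 9.

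**Infusions through Cycle 6, four-dose loncastuximab regimen**

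| Infusion | Visit | Day | Last scheduled panel | Panel age (days) |
|---|---|---|---|---|
| Loncastuximab 1 | C1D1 | 1 | Day 1 (or screening, up to 3 days earlier) | 0 (up to 3) |
| Durvalumab 1 | C1D8 | 8 | Day 8 | 0 |
| Loncastuximab 2 | C2D1 | 22 | Day 22 | 0 |
| **Durvalumab 2** | **C2D15** | **36** | **Day 29 (C2D8)** | **7** |
| Durvalumab 3 | C3D1 | 64 | Day 64 | 0 |
| Durvalumab 4 | C4D1 | 92 | Day 92 | 0 |
| Durvalumab 5 | C5D1 | 120 | Day 120 | 0 |
| **Loncastuximab 3** | **C5D8** | **127** | **Day 120 (C5D1)** | **7** |
| Durvalumab 6 | C6D1 | 148 | Day 148 | 0 |
| **Loncastuximab 4** | **C6D8** | **155** | **Day 148 (C6D1)** | **7** |

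**Count.** There are 4 loncastuximab and 6 durvalumab infusions, 10 in all. Seven have a same-day panel marked and 3 do not; 2 of those 3 are among the 4 loncastuximab doses.

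**Other denominators.** Over a year, durvalumab continues to C13D1 = 64 + 10 × 28 = Day 344, giving 13 durvalumab doses. The count is then 3 of 17 with four loncastuximab doses, or 1 of 15 with only the first two.

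**Effect of visit windows.** If both visits sit at their limits, panel age runs from 7 − 4 = 3 to 7 + 4 = 11 days.

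**Next panel after doses 3 and 4.** 148 − 127 = 176 − 155 = 21 days, or 17 to 25 with windows.

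**DLT window.** It covers the 21 days after the first durvalumab dose, nominally Day 8 to 8 + 21 = Day 29. All three infusions come later, the first on Day 36. With C1D8 two days late (Day 10) and C2D15 two days early (Day 34), the window ends on Day 31, still before the infusion.

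**Footnote 4.** The screening waiver mark is also printed on the C2D1 cell. Applied literally there, it would let a screening panel replace the C2D1 panel about 3 weeks later. It looks misplaced, and the C2D1 panel is counted here as scheduled.

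**The case against.** The best counter-argument is that the existing panels already cover most of the risk. Each preceding panel falls at least 21 days after the previous dose of the drug about to be given: Day 29 − 8 = 21 for durvalumab dose 2, 120 − 22 = 98 for loncastuximab dose 3, and 148 − 127 = 21 for dose 4. Only a new, silent abnormality arising in the last week goes unseen, and the documents give no rate for that.

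Neither 6.5.1 nor 6.5.2 demands a panel on the infusion day, so no text is contradicted. Investigators may draw unscheduled samples. Appendix 3 calls for liver tests every 1 to 2 days at Grade 2, and creatinine weekly at Grade 1 and every 2 to 3 days at Grade 2. Appendix 3 also exempts non-immune laboratory changes judged clinically insignificant from dose modification. Weight is measured a week earlier, patients are asked to weigh themselves daily, and SAP 4.7.1 uses the last weight available. Doses 3 and 4 are optional, and the trial stopped early.

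Most of this limits the size of the problem without closing the gap. Appendix 3 helps once an abnormality is known; for Grade 1 liver elevations it returns the site to protocol monitoring, which is the schedule in question. Section 6.5.1 sets no repeat-testing rule. The 98-day and 21-day intervals for doses 3 and 4 concern loncastuximab and leave out the durvalumab given on Day 1 of the same cycle. The weight element is the weaker part, and C2D15 is the stronger one because it affects every patient who continues to that visit.

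**Conclusion.** The gap is real and consists of exactly three infusions: C2D15, C5D8 and C6D8. At each, the latest scheduled panel is nominally 7 days old (3 to 11 with windows) while lab-triggered holds apply. This is a weakness in the safety schedule. It does not bias an endpoint, and nothing in the documents shows that a patient was harmed.

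The 3-of-10 figure assumes all four loncastuximab doses and a count ending at Cycle 6; a patient without the optional doses has one such infusion. The calendar assumes no dose delays. SAP 3.3 limits analysis to Part 1 after early termination, so the practical relevance is to patients who reached these doses and to any reuse of the schedule. Given the small cost, the change should be made wherever the schedule is used again.

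**What to change.** Mark hematology and chemistry before the infusion at C2D15. Add a Day 8 entry for Cycles 5 and 6, for patients receiving loncastuximab, with pre-infusion hematology, chemistry and weight. For the panels, one sentence in 8.3.5 requiring hematology and chemistry before every infusion, parallel to the vital-signs rule in 8.3.4, would do the same job; weight at C5D8 and C6D8 would still need its own mark. The stray footnote 4 on the C2D1 cell can be removed in the same edit.

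The cost is a table edit or one sentence, and up to three routine draws per patient at visits that already take place. C2D15 already includes PK sampling.

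These draws do not shorten the nominal 21 days to the next panel after doses 3 and 4. Matching the check made 7 days after doses 1 and 2 would need C5D15 and C6D15 visits, up to two extra per patient. That is optional and separate from the core change.

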6.4.2 Dose Limiting Toxicity Period

For patients in Part 1, the DLT period will be the 21 days after the first durvalumab dose. Any treatment-related toxicities that first occurred during the DLT period must be followed for resolution to determine if they qualify as a DLT as specified in the DLT criteria below.

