6.4.3 Dose Limiting Toxicity Definition

A DLT defined as any of the following events, which occur during the 21-day DLT evaluation period of Part 1, except those that are clearly due to underlying disease or extraneous causes:

A **hematologic** DLT is defined as:

- Grade 4 anemia
- Grade 3 anemia requiring transfusion
- Grade 4 neutropenia lasting > 7 days
- Febrile neutropenia
- Grade 4 thrombocytopenia
- Grade 3 thrombocytopenia which results in clinically significant bleeding or requires a transfusion

A **non-hematologic** DLT is defined as:

- Hy's law case - AST and/or ALT $\geq 3 \times$ ULN and bilirubin $\geq 2 \times$ ULN, and without initial findings of cholestasis (serum alkaline phosphatase [ALP] activity $< 2 \times$ ULN) and no other reason that could explain the combination of increased transaminases and serum total bilirubin
- Any other non-hematologic toxicity \geq Grade 3 with the exception of the following:
 - Grade 3 fatigue for ≤ 7 days.
 - Grade 3 nausea, vomiting, or diarrhea in the absence of premedication that responds to therapy and improves by at least 1 grade within 3 days or to \leq Grade 1 within 7 days.
 - Grade 3 elevations of ALP and GGT elevations, unless considered clinically relevant by the Investigator.
 - Grade 3 elevation of serum lipase or serum amylase for ≤ 7 days if without clinical signs or symptoms of pancreatitis.
 - Grade 3 electrolyte abnormalities that normalize within 48 hours (with or without medical intervention) and that do not manifest themselves clinically; in such instance, a follow-up sample MUST be taken within 48 hours to check whether such normalization has occurred.

- In addition, the following will be considered DLTs:
 - Grade 2 noninfectious pneumonitis that does not resolve to \leq Grade 1 within 3 days of the initiation of maximal supportive care
 - Any grade of immune-mediated rash with bullous formation
 - Grade 2 or 3 immune-mediated peripheral neuromotor syndrome (such as Guillain-Barre and myasthenia gravis) that does not resolve to Grade \leq 1 within 30 days or that exhibits signs of respiratory insufficiency or autonomic instability
 - Grade 2 immune-mediated myocarditis that does not resolve to Grade \leq 1 within 3 days of initiating optimal medical management, including systemic corticosteroids

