8.3.6 Pregnancy Test

A highly sensitive β -HCG test in urine or blood β -HCG test must be performed in women of childbearing potential (WOCBP) for eligibility (see [Section 5.1](#)) and throughout the study as per SoE.

The C1D1 pre-dose pregnancy test can be waived if the test for eligibility was done within 3 days of C1D1. After starting the study drug, all efforts should be made to keep the interval between 2 consecutive pregnancy tests no more than 6 weeks.

If a pregnancy test is positive, study drug must be held pending confirmation. If the pregnancy is confirmed, treatment must be discontinued permanently for the patient. Refer to [Section 8.2.6](#) for the handling of the patient and reporting the event.

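### Scheduled hematology/chemistry in the 21-day DLT window is sparse, and a C1D1 lab waiver is also printed on C2D1, so short silent laboratory DLTs may be missed

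*Protocol*

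**What the plan says.** Protocol 6.4.2 sets the window: "For patients in Part 1, the DLT period will be the 21 days after the first durvalumab dose". Section 6.3.2 puts that dose on Day 8 of Cycle 1. Section 8.3 has safety assessments on dosing days done before study drug, unless otherwise specified. Section 8.3.5 refers laboratory timing to Table 1 and adds no separate schedule for the DLT period.

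In Table 1 the hematology/chemistry row is ticked at screening, at Days 1 and 8 of Cycles 1 and 2, at Day 1 of later cycles and at EOT. The Day 15 cells of Cycles 1 and 2 are blank. Footnote 4 is attached to both C1D1 and C2D1 in this row and reads "Not needed if screening assessment was performed within 3 days prior to C1D1". The pregnancy-test row carries the same footnote on C1D1 only, and section 8.3.6 gives that scope in words: "The C1D1 pre-dose pregnancy test can be waived if the test for eligibility was done within 3 days of C1D1".

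Section 6.4.3 counts "Grade 4 thrombocytopenia" as a DLT with no minimum duration. Section 6.5.1 requires that, after Grade 3 or higher toxicity (Grade 2 or higher for edema, effusion or AST/ALT/GGT), "loncastuximab tesirine must be held until the toxicity resolves to Grade 1 or less".

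**The concern.** Several DLTs are found only by a blood test. Grade 4 thrombocytopenia counts at any duration. Grade 3 ALT or AST elevation is not among the listed exceptions, which for liver enzymes cover only ALP and GGT. With long stretches between scheduled draws, such an event can start and recover unseen, and every miss lowers the DLT count. In a 3+3 design one missed event turns 1 of 3 into 0 of 3, and the dose escalates without the three extra patients. It turns 2 of 3 into 1 of 3, and the cohort expands instead of the preceding dose being declared the MTD.

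The risk fits this drug: protocol 1.2.2 reports three patients with a DLT in the single-agent study, two of them with thrombocytopenia.

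The footnote on C2D1 adds a dosing problem. Taken literally, a screening sample about three weeks old would replace the values needed to apply the 6.5.1 hold before the second loncastuximab dose.

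**Working it through.** The plan gives no figure for this, so the check is calendar arithmetic followed by an illustration.

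**Calendar** (Cycle 1 is 21 days and Cycle 2 is 42 days, protocol 4.3)
- C1D8 = Day 8; C1D15 = Day 15; C2D1 = 1 + 21 = Day 22; C2D8 = Day 29; C2D15 = Day 36; C3D1 = 22 + 42 = Day 64.
- Cross-check on the 4-week durvalumab interval: 36 − 8 = 28 and 64 − 36 = 28.
- DLT window: Day 8 + 1 to Day 8 + 21, that is Days 9-29.

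**Scheduled draws in the window and longest stretch without one**
- As ticked: Days 22 and 29. Longest stretch is Days 9-21, 13 days.
- C2D1 waived: Day 29 only. Longest stretch is Days 9-28, 20 days.
- C1D15 added: Days 15, 22 and 29. Longest stretch is 6 days.

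**Chance that a scheduled draw falls inside an episode.** Assumptions, because the documents give neither onset nor duration: onset equally likely on each of the 21 days 9-29, visits on time, no unscheduled labs. A d-day episode starting on day s covers days s to s + d − 1. The count is the number of the 21 onset days for which that span contains a draw.

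| Episode | As ticked {22, 29} | C2D1 waived {29} | C1D15 added {15, 22, 29} |
|---|---|---|---|
| 3 days | 6/21 = 29% | 3/21 = 14% | 9/21 = 43% |
| 5 days | 10/21 = 48% | 5/21 = 24% | 15/21 = 71% |
| 7 days | 14/21 = 67% | 7/21 = 33% | 21/21 = 100% |
| 10 days | 17/21 = 81% | 10/21 = 48% | 21/21 = 100% |

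As ticked, an episode of 14 days or more is always met: one starting on Day 9 reaches Day 22.

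One draw inside an episode is not full ascertainment. Days 22 and 29 are exactly 7 days apart, so two scheduled values cannot by themselves establish Grade 4 neutropenia of more than 7 days; that needs follow-up draws.

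**Visit windows.** Treatment visits may move by ±2 days, counted from C1D1. Let a be the offset of C1D8 and b that of C2D8. The window ends on Day 29 + a and C2D8 falls on Day 29 + b, so C2D8 is outside the window when b > a. That holds for 4 + 3 + 2 + 1 + 0 = 10 of the 25 whole-day pairs (a count, not a probability). In those pairs one in-window draw remains as ticked, and none if C2D1 is waived.

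**Possible effect on escalation (illustration).** Assume a true DLT rate of 33%, with half of DLTs silent laboratory events lasting 7 days. P(escalate) = (1 − p)³ + 3p(1 − p)² × (1 − p)³, where p is the observed rate.
- Full detection: p = 0.33, P = 43%.
- As ticked (miss 7/21): p = 0.33 × (1 − 0.5 × 1/3) = 0.275, P = 55%.
- C2D1 waived (miss 14/21): p = 0.33 × (1 − 0.5 × 2/3) = 0.22, P = 67%.
- C1D15 added (miss 0): p = 0.33, P = 43%.

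**The case against.** - **The footnote is probably a misprint.** The pregnancy row, section 8.3.6 and the 6.5.1 hold all point to current labs before C2D1. This stands, so the waived-C2D1 figures describe a literal reading, not the likely practice. The blank C1D15 cell is the firmer half of the point and does not depend on the footnote. Weight and vital signs are ticked in that same column, so a table-reading error is unlikely there.
- **Onset and duration are assumed.** This also stands. The percentages show scale only. A draw that catches a count still recovering at Grade 2-3 gets no credit in the table, although it could prompt further inquiry.
- **The ±2-day windows also weaken the fix.** Correct: C1D15 and C2D1 could be 11 days apart (Day 13 to Day 24), so the 100% entries hold only for on-time visits. A C2D8 draw just after the window may still reveal an event that began inside it.
- **Other safeguards exist.** Fever, bleeding and transfusion come to notice clinically. Unscheduled labs enter the worst-case summaries, and the steering committee reviews safety at least monthly. But follow-up under 6.4.2 begins only once an abnormality is known, and none of these schedules a draw in the gap. Silent short events remain exposed.
- **The trial ended early.** SAP 3.3 says so, and a schedule change cannot recover days that were not sampled. The SAP already lists all laboratory and infusion data, so the suggested extra listing columns are a convenience rather than new information.

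**Conclusion.** The concern holds as a design weakness with an inexpensive remedy. As ticked, the DLT window contains two scheduled hematology/chemistry draws, the first 14 days after durvalumab and the second on the last day. Literal use of footnote 4 leaves only the second. Under uniform onset and on-time visits, a scheduled draw meets 29% of 3-day, 48% of 5-day and 67% of 7-day episodes. The bias runs one way, toward fewer observed DLTs. Its true size is unknown, because the documents give no onset or duration data and unscheduled labs may have filled part of the gap. It concerns only laboratory events without symptoms that recover between draws.

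Two neighbouring points in Table 1 concern dosing safety and do not affect DLT counts. C2D15 is a durvalumab day, yet no hematology/chemistry is scheduled between Day 29 and Day 64. The premedication cell for later cycles says D-1 to D2, whereas loncastuximab in Cycles 5 and 6 is given on Day 8 and section 6.7.1 ties premedication to that administration.

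**What to change.** 1. Remove footnote 4 from the C2D1 hematology/chemistry cell.
2. Tick hematology/chemistry at C1D15, where blood is already taken for PK and ADA.
3. As a separate dosing-safety correction, tick it pre-dose at C2D15, where PK blood is already taken, and align the Cycle 5/6 premedication cell with the Day 8 loncastuximab dose as in section 6.7.1.
4. If dosing has ended, add to the DLT listing in SAP 4.8.1 the actual hematology/chemistry dates from the first durvalumab date to 21 days after it, and mark patients without C2D1 labs. A reader can then tell whether the absence of a laboratory DLT was observed or merely unmeasured.

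Items 1-3 cost a wording change and two routine safety tubes at visits that already have a venipuncture, with no extra visits. Item 4 costs a few columns in one listing, built from data already collected.
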